Intervention/control group: The intervention was the ward working according to the Comprehensive Geriatric Assessment. Key components of the CGA are multi-disciplinary teamwork, use of a personcentred approach, comprehensive assessments, treatment and rehabilitation, discharge planning and follow-up. The multi-disciplinary team consisted of a physician, registered nurse (RN), assistant nurse (AN), physiotherapist (PT) and occupational therapist (OT) as well as other team members, such as a social worker (SW) and dietician, if needed. The control group received the usual acute hospital care, i.e., care given at an ordinary medical hospital ward without a specialised multi-disciplinary team approach and without the CGA. The assessments and care provided at the control wards were based on the acute problem/symptom that the patients had and did not include the comprehensive and person-centred approach to the health and life situation of the patient inherent in a CGA.

Measurements: Dependence in daily activities was measured using the ADL-staircase assessment by combining both interviews and observations. It includes dependence in nine activities: cleaning, shopping, transportation, cooking, bathing, dressing, going to the toilet, transferring and feeding. Dependence was defined as a state in which another person is involved in the activity by giving personal or directive assistance. The sum of dependence in the nine activities of daily living is calculated, range 0−9, with a clinically significant change of ≥1 unit between baseline and follow-up.

Functional status was measured using the Timed Up and Go (TUG) test, the Berg Balance Scale, Gait Speed four-metre walking test and Grip Strength with North Coast Dynamometer. The TUG test measures the time for a person to rise from a chair, walk 3 m, turn around, walk back,

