and sit down again. It measures both static and dynamic balance. In this study, we defined a change of ≥ 4 s as a clinically significant difference between baseline and follow-up, with 3.6 s considered as the minimal detectable change for TUG test measurements. For details on Berg Balance Scale, Gait Speed and Grip Strength, Cognition was measured using the Mini Mental State Examination. Self-rated was measured by the question: "In general, would you say your health is", with the response alternatives: excellent, very good, good, fair, and poor. Clinically significant difference was defined as ≥ 1 step in the response alternatives between baseline and follow-up. In addition, self-reported symptoms were measured using the Göteborg Quality of Life Instrument.

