Life satisfaction was measured using the Fugl-Meyer-Lisat-11 Questionnaire which includes 11 items concerning satisfaction with: life as a whole, work, financial situation, leisure, friends and acquaintances, sexual life, functional capacity, family life, partner relationship, physical health and psychological health. Response alternatives included: very dissatisfied, dissatisfied, rather dissatisfied, rather satisfied, satisfied and very satisfied. In the analysis, the responses to each question were dichotomised into satisfied (very satisfied and satisfied) or not satisfied (rather satisfied, rather dissatisfied, dissatisfied and very dissatisfied) as was done in the validation of the questionnaire. The sum of items for which the respondent reported being satisfied were calculated, range 0–11, with a clinically significant change of ≥1 between baseline and follow-up. Satisfaction with quality of care was measured by the participant's agreement with six statements with a person-centred approach: "I feel that the care given during the hospital stay meets my needs", "I feel that the care planning meeting before discharge was valuable", "I was able to take part in the discussion of my needs in the care planning meeting", "I feel that the actions planned equal my needs", "I feel that the actions delivered equal my needs" and "I am satisfied with the hospital care". The response alternatives were agree completely, agree partly, neither agree nor disagree, disagree, and disagree completely. An answer of agree completely or agree partly were considered as satisfied. These questions were only measured once (at 1 month follow-up) and were used as the difference between intervention and control groups in the proportion of participants being satisfied for each question at follow-up as has been done previously. In this study, we used the following measurements and cut-off levels of frailty indicators: Weakness: Reduced grip strength considered to be below lowest norm range for ages 80-84, 13 kg for women and 21 kg for men for the right hand and below 10 kg for women and 18 kg for men for the left hand, using a North Coast dynamometer. Fatigue: Question from the Göteborg Quality of Life Instrument, answering "Yes" to the question "Have you suffered any general fatigue/tiredness over the last three months?"

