Weight loss: Question from the Göteborg Quality of Life Instrument, answering "Yes" to the question "Have you suffered any weight loss over the last three months?"

Reduced physical activity: Taking 1–2 or less outdoor walks per week.

Impaired balance: The Berg Balance Scale, reduced balance defined as having a value of 47 or less. Reduced gait speed: Walking four metres with a gait speed of 0.6 metres/second or slower. Visual impairment: The KM chart (Konstantin Moutakis chart), impaired vision defined as having a visual acuity of 0.5 or less.

Impaired cognition: The MMSE, impaired cognition defined as having a score below 25.

Statistical analysis

A power calculation was done based on the primary outcome variable, dependence in activities of daily living (range 0–9) with an assumed difference between the intervention and control groups of one dependence (i.e., dependent in one or more activities of daily living, a clinically relevant difference of importance to the individual as well as the caregiver) and a standard deviation of 2 in both groups. To detect a difference between the intervention and control groups with a two-sided test and with a significance level of α = 0.05 and 80% power, at least 64 participants were needed in each group. To take a potential loss to follow-up into account, a total of 150 persons (75 in the control group and 75 in the intervention group) were initially planned to be included. This was later revised to allow for a higher loss to follow-up (22%) with 78 + 78, equalling a total of 156 participants.

Both descriptive and analytical statistics were used in order to compare groups and to analyse changes over time. Non-parametric statistics were used when ordinal data were analysed. Otherwise, parametric statistics were used. Besides descriptive statistics, the chi^2 and Fisher's two-tailed exact tests to test differences in the proportions among the groups were used. A value of $p \le 0.05$ (two-tailed) were considered significant. The analysis were made on the basis of the intention-to-treat principle, meaning that participants were analysed on the basis of the group to which they were initially randomised. The approach of data imputation was the replacement of missing values with a value based on the median change of deterioration between baseline and follow-up of all who participated in the follow-up.

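### Filling missing follow-up values from one median change pooled over both arms shrinks the estimated effect and overstates its precision; if ≥1-unit changes are compared on filled data, clearly unequal loss can also create a false difference

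*Combined protocol and SAP*

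**What the plan says.** All references are to the combined protocol and SAP.

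- **Imputation (Statistical analysis, last paragraph).** Missing values are replaced by "a value based on the median change of deterioration between baseline and follow-up of all who participated in the follow-up". The donors are not split by arm. No missing-data assumption, complete-case comparison or sensitivity analysis is given. The analysis follows the intention-to-treat principle.
- **Tests (same section).** "Non-parametric statistics were used when ordinal data were analysed"; other data are analysed parametrically. For proportions, chi-square and Fisher's "exact tests to test differences in the proportions among the groups were used". No mean difference or confidence interval is named for ADL.
- **Change thresholds (Measurements).** The ADL sum is described "with a clinically significant change of ≥1 unit between baseline and follow-up". For self-rated health, "Clinically significant difference was defined as ≥ 1 step in the response alternatives between baseline and follow-up". Life satisfaction is described "with a clinically significant change of ≥1 between baseline and follow-up".
- **Between-arm proportions (Measurements).** The only such comparison spelled out is satisfaction with care: the "difference between intervention and control groups in the proportion of participants being satisfied for each question at follow-up". It is measured once, at 1 month, and has no baseline.
- **Sample size (Statistical analysis).** Difference of one activity, SD 2, two-sided 5% level, 80% power, 64 per group; later 78 per group, to allow for 22% loss.

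**The concern.** Giving every missing participant the same change, whichever arm they belong to, pulls the two arms towards each other. One activity on the ADL sum is the difference the trial was sized to detect and calls clinically relevant. A true effect of that size could therefore be reported as smaller, with an interval that is too narrow.

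Thresholds raise a second issue. One filled change puts nearly all missing participants on the same side of a ≥1-unit cut. If the arms lose clearly different fractions, the filled proportions can then differ with no true effect.

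The wording of the rule is also unclear. It can mean the median of all changes, or the median among those who deteriorated, and the two behave differently.

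**Working it through.** **Inputs from the plan:** difference 1, SD 2, 78 per arm, 22% loss. **Assumptions:** SD 2 applies to change (the plan does not say so); control drift 0.3 or 1.0; loss by arm is illustrative; a ≥1-unit change means worsening. Unless stated, simulations use normal changes, random loss and 4,000 runs, and ranges cover both drifts.

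**1. The plan's own figure.** n = 2 × (1.960 + 0.842)² × 2² / 1² = 62.8, so 63 by the normal approximation. The t-test version gives 63.8, so 64. The stated 64 is reproduced.

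**2. Equal random loss d, common filled change M.** Each filled arm mean is (1 − d)μ + dM. The difference is (1 − d)(μ_C − μ_I), whatever M is.

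- d = 0.22: 0.78 × 1 = 0.78
- d = 0.179 (78 down to 64): 0.82
- d = 0.147 (75 down to 64): 0.85

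Simulation at 22% gives 0.77–0.78. On an integer 0–9 ADL scale, the filled difference is 74–79% of the true one across the loss splits tried. The Hodges-Lehmann shift that goes with a rank test falls to 0.61–0.62 (completers 0.99–1.01).

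**3. Precision and tests at 22% in both arms.** With M midway between the arm means, the filled variance is 0.78 × 4 + 0.22 × 0.78 × 0.5² = 3.16, so the SD is 1.78. The standard error is 1.78 × √(2/78) = 0.285 and the half-width 1.96 × 0.285 = 0.56. For completers (78 × 0.78 = 60.84 per arm) the standard error is 2 × √(2/60.84) = 0.363 and the half-width 0.71. Estimate and standard error shrink by nearly the same factor: 0.78/0.285 = 2.74 against 1/0.363 = 2.76. The test statistic hardly moves.

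The interval is centred 0.22/0.285 = 0.77 standard errors too low, so coverage is Φ(1.19) − Φ(−2.73) = 0.88. Simulation gives 0.875–0.876. Simulated power is 78% for the t-test (completers 78%) and 73% for Mann-Whitney (completers 76%). Null rejection for Mann-Whitney is 4.2–5.8% at every split tried, from 22%/22% to 10%/34%.

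**4. Unequal random loss.** The expected difference is δ − d_C(μ_C − M) − d_I(M − μ_I). At 12% versus 32%, with M anywhere between the arm means, it lies between 1 − 0.32 = 0.68 and 1 − 0.12 = 0.88.

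**5. Change ≥1 compared on filled data.** The filled proportion is (1 − d)p + d × I(M ≥ 1). With no true effect, control minus intervention is (d_C − d_I) × (I(M ≥ 1) − p). With control losing 29% and intervention 15%, this is 0.14 × (0 − 0.40) = −5.6 points if M < 1 and p = 0.40, or 0.14 × (1 − 0.60) = +5.6 points if M ≥ 1 and p = 0.60. Swapping the losses swaps the signs.

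| Null rejection, change ≥1 | Chi-square | Fisher |
|---|---|---|
| 22% / 22% | about 5% | 3.4% |
| 20% / 24% | 5–6% | 4–5% |
| 15% / 29% | 11–14% | 7.5–11% |

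Completers' chi-square stays at 5–6%.

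| Risk difference, true mean difference 1 | Normal | Integer 0–9 |
|---|---|---|
| Completers | 0.17–0.19 | 0.18–0.20 |
| Filled, 22% in both arms | 0.13–0.15 | – |
| Filled, control loses 29%, intervention 15% | 0.09–0.10 | 0.09–0.13 |
| Filled, intervention loses 29%, control 15% | 0.17–0.20 | 0.15–0.19 |

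Clear inflation needs greater imbalance. With assumed proportions 0.35 and 0.55 (20 points) and loss of 10% versus 34%, the filled difference ranges from 2.4 to 28.8 points.

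**6. Median among deteriorators only, 15% versus 29%** (3,000 runs). Null rejection is 7–12% (t-test), 7–14% (Mann-Whitney) and 11–19% (chi-square). The estimated mean difference is 49–106% of the true one, depending on which arm loses more.

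**The case against.** **The plan names none of the distorted quantities.** It specifies no mean difference, interval or rank-based shift for ADL. Under random loss and the all-changes median, the tests it does allow keep their level and lose little power, and the shrinkage leans towards no effect. This stands, and it confines the harm to the reported effect size and its precision. A reader might infer that the rule invalidates the trial's t-tests or rank tests; the documents do not support that.

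**The threshold comparison is inferred.** The plan defines ≥1-unit changes and lists tests of proportions, but never says the one is applied to the other on filled data. Satisfaction with care, the comparison it does spell out, has no baseline to which a median change could be added. This stands, so the point is conditional.

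**Inflation is weakly supported.** At 15% versus 29% it is slight, and on the integer scale it reverses with drift. This stands.

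**Loss that depends on decline is a separate problem.** A reader might infer that false positives arise only with unequal loss rates, or that the pooled rule is what causes them. Neither holds. With 22% loss in both arms, but dependent on final change in the control arm only, simulated null rejection was about 17–20% (t-test) and 15–17% (Mann-Whitney). Completers' t-test rejected equally often, so this is not caused by the pooled rule.

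**A value based on a median need not be one constant.** The rule leaves visit, baseline handling and rounding open. The figures above rest on the common-change reading, which is the natural one, and this openness is itself a reason to state the rule fully.

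**An analysis added after data collection should not displace the stated one.** Accepted; the fix keeps the stated analysis.

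**Conclusion.** The concern holds in limited form. Followed as written and read as one common filled change, the rule attenuates a mean difference by the missing fraction under equal random loss: about 0.78 for a true 1.0 at 22%, with about 88% coverage from a nominal 95% interval. A rank-based shift shrinks too. The 22% is a planning allowance, not observed loss.

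If ≥1-unit or ≥1-step categories are compared on filled data, balanced loss shrinks the risk difference. Clearly unequal loss can create a false one or strongly shrink a true one. At 20% versus 24% the effect on type I error is negligible. Under the deteriorators-only reading, unequal loss also biases mean and rank comparisons, so the wording needs settling in any case.

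A reader might go further and conclude that the trial's reported effect is biased by a known amount or in a known direction. The documents give neither loss by arm nor the observed median, so they do not support that.

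**What to change.** 1. Keep the stated pooled-median analysis and say which median it uses. State that its effect size is expected to be attenuated and its interval too narrow.
2. Report loss by arm and visit with reasons, including deaths, and say how values missing because of death are handled.
3. Beside it, report the ADL effect with its interval from multiple imputation within arm, conditional on baseline and, where they exist, earlier visits, combined by Rubin's rules. At 1 month there is no earlier follow-up visit. A likelihood-based repeated-measures or ordinal model of the 1-, 6- and 12-month values would also serve. Derive any ≥1-unit categories from the multiply imputed values.
4. Label this as added after data collection, and add a version with imputed values shifted by arm.

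**Cost.** SAP wording and a re-run on existing data. In simulation (2,000 runs, 20 imputations, one earlier visit) the half-width rises from about 0.56 to about 0.69. Under random loss, multiple imputation gives 0.99–1.01 with 95–96% coverage.

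It assumes data missing at random and is not better in every scenario. When loss depends on the unseen final change in the same way in both arms, the estimates of a true 1.0 are:

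| Loss | Pooled median | Multiple imputation |
|---|---|---|
| 22% in both arms | 0.78 | 1.00–1.01 |
| Control 29%, intervention 15% | 0.60–0.61 | 0.87–0.88 |
| Intervention 29%, control 15% | 0.94–0.95 | 1.12 |

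In the last row the pooled rule is nearer the truth, which is why the arm-shifted version is needed.
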